	Yes	8	Yes	8	Yes	2	Yes	Q	Yes	2	Yes	Q	× ×	2
Antibiotic/Antifungal drugs													3	
Laxative drugs														
Antidiarrheal drugs														
Other drugs														
If Yes , please write the name of drugs														
Check point	Put ice packs in the freezer	packs reezer												
Memo in case the specimen is NOT obtained.								84

Probiotics are being used with increasing frequency in medicine and by the general population given the increasing evidence on the beneficial effects on human health. The probiotic efficacy relies on their ability to survive in the digestive system and then to proliferate in the gut. Factors related to survivability in the GI tract include the probiotic strain, as well as other intrinsic and extrinsic factors, and the ability to survive in the GI tract varies considerably among lactobacilli species. Ingested bacteria are exposed to adverse conditions starting as soon as they reach the stomach, with survival influenced by the time required to leave the stomach. The gastric emptying rate, therefore, is an important feature for the survival of bacteria. Factors such as type and composition of food consumed, lifestyle age, environment and race are known to influence the gastric emptying rate and, thus, influence the survival of the probiotic bacteria. The small intestine, especially its proximal part, contains hydrolytic enzymes and bile salts known to have a lethal effect on microorganisms. Thus, ability to pass easily through this compartment of the GI tract may also substantially affect the survival of ingested bacteria.

[figure not shown]
The aim of this study is to investigate the survival of LcS in the intestine of generally healthy adults after intake of fermented milk (Yakult). Similar studies have been conducted by other investigators. For example, clinical studies conducted in Japan, Vietnam, China, and the United Kingdom have reported on the survival of LcS in the intestine in healthy adults. The study described in this proposal is intended to investigate whether the survival of LcS is the same or not in generally healthy adults in the U.S., who may have different ethnicities (e.g., genetic factors), as well as lifestyles, food habits, and environmental influences compared to these previous studies

3. Study objectives

The objective of this study is to investigate the survival of LcS in the human GI tract after consumption of fermented milk in generally healthy adults, 18 to 40 years of age (inclusive), with a body mass index (BMI) \geq 18.5 and \leq 29.9 kg/m².

4. Trial design and visit structure

This is a single-arm, open label study with one screening visit (Visit 1; Day 0), one baseline visit (Visit 2; Day 14), two intervention visits (Visit 3 and 4; Days 21 and 28), and one post-intervention follow-up visit (Visit 5; Day 42).

Eligible subjects will be enrolled and start a 14-d run-in period (baseline) with the instruction to avoid fermented dairy and non-dairy products. Participants will be instructed to collect a stool sample sometime after 7pm the day before and prior to the next visit (Visit 2; Day 14). Visit 2 (Day 14) is the end of the run-in and start of the ingestion period. The first serving of the study product will be consumed during the clinic visit after participants have consumed breakfast (at home) and obtained/dropped off their stool samples. Subjects will be instructed to consume 1 bottle of study product within 30 minutes of breakfast every day. Additional stool samples will be collected at visit 3 (Day 21), Visit 4 (Day 28), and Visit 5 (Day 42). Pertinent data collection points are presented below in the abbreviated flow chart.

Abbreviated Flow Chart						
	Screening/ Start Run-in	End Run-in/ Start Study Product	Interim Study Visit	End Product/ Start Follow-up	End Follow- up	
Visit	1	2	3	4	5	
Days	0	14	21	28	42	
Clinic Visit	X	X		X	X	
Study Instructions & Query	X	X	X	X	X	
Review Daily Diary	X	X	X	X	X	
Dispense Fecal Collection Kit	X	X	X	X		
Fecal Collection Kit Returned		X	X	X	X	
Compliance			X	X		
Adverse Events		X	X	X	X	

The daily dairy will capture the date and time of daily product consumption, the occurrence of any of adverse events (AEs), concomitant medication use, and compliance to diet restrictions (no fermented foods or probiotic supplements).

5. Definition of endpoint measures

5.1. Primary endpoint

Change in LcS number (CFU/g feces) from baseline (Visit 2; Day 14) to the end of the ingestion period (Visit 4; Day 28). Bacterial count will be conducted at Institute for Food Safety and Health (IFSH; Bedford Park, IL) using the culture method (FOM-LLV) and PCR approaches, and reported as CFU/g feces.

5.2. Secondary endpoint(s)

- Change in LcS number (CFU/g feces) from baseline (Visit 2; Day 14) to during the ingestion period (Visit 3; Day 21).
- Change in LcS from the end of the ingestion period (Visit 4; Day 28) and to the end of follow-up (Visit 5; Day 42)

5.3. Safety outcome endpoint(s)

- Overall incidence of product-emergent AEs
- Number, type, and duration of Serious Adverse Events (SAEs)

6. Definitions of analysis sets

6.1. Intent-to-treat (ITT) population

The intent-to-treat (ITT) population includes all subjects who were enrolled and serves as the primary analysis population

6.2. Per protocol (PP) population

The per protocol (PP) population is a subset of the ITT population in which subjects will be excluded for, but not limited to, the following reasons:

- Missing consumption of product for two or more days during study product ingestion period
- Not consuming the study product the day before stool collection
- Missing appointments
- Use of prohibited drugs or any products thought to alter the primary outcome variable during the study
- Not adhering to instructions as outlined in the protocol

All decisions regarding the exclusions from the PP population will be documented following the data review meeting which will occur prior to database lock.

7. Determination of sample size

Sample size was determined based on previous studies, which indicate enrolling a sample size of N=25 will provide sufficient data for a significant effect. No subjects will be replaced in the event of early terminations.

8. Statistical methods

Unadjusted descriptive statistics will be provided per measured time point. Continuous variables will be summarized with mean, standard deviation, median, and range. Categorical variables will be summarized with counts and percentages. All tests of significance are two-sided and considered significant at the 0.05 level. SAS (version 9.4 or higher) or R (version 4.2.0 or higher) will be used for statistical analyses. All analyses will be conducted for the ITT and PP populations.

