The primary outcome variable will be the change in live LcS numbers (CFU/g feces) from baseline (Visit 2; Day 14) to the end of the ingestion period (Visit 4; Day 28).

Secondary Outcome Variables

- Change in LcS number from baseline (Visit 2; Day 14) to during the ingestion period (Visit 3; Day 21).
- Change in LcS from the end of the ingestion period (Visit 4; Day 28) and to the end of follow-up (Visit 5; Day 42)

Safety Outcomes

Safety will be assessed by:

- Overall incidence of product-emergent AEs
- Number, types and duration of Serious Adverse Events (SAEs)

STATISTICAL ANALYSIS	The safety analysis will be conducted based on the modified Intention-to-Treat (ITT) population defined as all participants who receive at least one serving of the study product. The efficacy analysis will be conducted on the Per Protocol (PP) population, defined as all participants who completed the intervention in compliance.	
	The LcS number (CFU/g feces) will be evaluated with a repeated measures model. The LcS number measured at each time point will be log-transformed and included in the response vector. The absolute change from baseline to each measured time point will be estimated along with the corresponding 95% confidence interval (CI). Non-detectable levels will be replaced by zero. In the event model assumptions are violated (i.e., constant variance and/or normality of residuals), a rank-based transformation will be considered.	
STUDY PERIOD	Baseline/ run-in period (between Visit 1 and Visit 2): 14 days Study product consumption period (Visit 2-Visit 4): 14 days Follow-up period (between Visit 4 and Visit 5): 14 days	

4. Background/Rationale

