12.3 Statistical Analysis

Statistical analysis details for this study will be provided in a Statistical Analysis Plan. Briefly, all statistical analyses will be conducted using SAS for Windows (version 9.4, or higher, Cary, NC) and/or R (R Core Team 2022). Analysis populations will include intent-to-treat (ITT; all subjects randomized in the study who have consumed at least one serving of the study product) and per protocol (PP; all subjects completing the study in compliance). Safety outcomes will be evaluated on the ITT population. The PP population will serve as the primary analysis population for efficacy outcomes.

Subjects may be excluded from the PP population for non-compliance, which includes but not limited to:

- Missing consumption of product for two or more days during study product ingestion period
- Not consuming the study product the day before stool collection
- Missing appointments
- Use of prohibited drugs or any products thought to alter the primary outcome variable during the study

Not adhering to instructions as outlined in the protocol

All decisions regarding subject population and data inclusion will be documented prior to database lock.

12.3.1 12.3.1 Baseline Characteristics

Descriptive statistics [number of subjects, mean, standard deviation (SD), standard error to the mean (SEM), median, interquartile limits, minimum and maximum or frequency counts] will be presented for subject demographics and anthropometric measurements at screening/baseline for all analysis populations.

12.3.2 12.3.2 Outcome Analysis

Bacterial count will be conducted at Institute for Food Safety and Health (IFSH; Bedford Park, IL) using the culture method (FOM-LLV) and PCR approaches, and reported as CFU/g feces. The LcS number will be evaluated with a repeated measures model. The LcS number measured at each time point will be included in the response vector. The absolute change from baseline to each measured time point will be estimated along with the corresponding 95% confidence interval. Non-detectable levels will be replaced by zero. In the event model assumptions are violated (i.e. constant variance and/or normality of residuals), a rank-based transformation or log transformation (if non-zero counts) will be considered.

12.3.3 12.3.3 Safety Analysis

All AEs will be collected; however, safety will be assessed by SAEs and productemergent AEs only as reported by the subjects, as well as an assessment of vital signs.

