8.1. Demographic and anthropometric measures

Subject demographic and anthropometric measures of enrolled subjects will include:

- Collected at screening visit 1
 - o Age (years)
 - o Sex (Male, Female)

- o Ethnicity (Hispanic/Latino, Not Hispanic/Latino)
- Race (White, Black/African American, Asian, Native Hawaiian/Other Pacific Islander, American Indian/Alaskan Native, Other). Note "more than one race" will be used if more than one race is selected
- o Weight (kg)
- o Height (cm)
- \circ BMI (kg/m²)
- o Heart rate (bpm)
- Systolic blood pressure (mmHg)
- Diastolic blood pressure (mmHg)

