8.2. Outcome analyses

For samples where LcS is not detected, counts will be set to the limit of detection to allow for statistical analysis¹. Descriptive plots will be provided for the distribution of LcS at each time point (i.e. boxplots) as well as line graphs for each subject. LcS number over time will be analyzed with a repeated measures model with an unstructured covariance structure where the LcS number at each time point will be included in the response vector. The model derived absolute change in LcS from baseline (day 14) to each of days 21, day 28, and 42 will be estimated along with the corresponding 95% confidence interval. In the event model assumptions are violated (i.e. constant variance and/or normality of residuals), a log transformation followed by a rank transformation will be considered. Note, if a rank transformation is used, contrast statements will be used to test the change from baseline but an estimate will not be calculated.

It is possible that the baseline LcS number for all subjects will be non-detectable which would likely result in the model assumption failure. If there are no detectable LcS levels at baseline and the repeated measure model assumptions are violated after exploring possible data transformations, then a model will be fit that only considers the post-consumption time points where the subject is on active product (day 21 and day 28). The estimated mean and 95% CI at day 21 and day 28 would then reflect an estimated increase from baseline. The proportion of subjects that return to baseline (day 14) by day 42 will be estimated along with a 95% CI. Additionally, in the subset of subjects that have elevated LcS while on study product measured at day 21 or day 28, as compared to baseline (day 14), the proportion of subjects that return to baseline by day 42 will be estimated along with a 95% CI.

Product emergent-AEs and SAE will be described. The proportion of subjects with at least 1 possibly, probably, or definitely related AE will be estimated along with the corresponding 95% CI.

9. Handling of missing data

For outcomes measured at multiple time points post baseline, statistical models that account for unbalanced data will be used. Specifically, missing data will be handled by maximum likelihood estimated of mixed models which assumes data is missing at random.

10. Deviations from statistical plan and other issues

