During the analysis and reporting process, any deviations from the statistical analysis designed for this protocol will be described and justified.

11. Changes from protocol

N/A

12. References

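### Read literally, the SAP puts the adverse-event outputs on all enrolled subjects and on PP, not on the protocol's at-least-one-serving set, and declares no change from protocol

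*SAP*

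**What the plan says.** **Protocol.** The Synopsis (section 3, Statistical Analysis) bases safety on a modified ITT population, "defined as all participants who receive at least one serving of the study product". Section 12.3 calls the set simply ITT but again requires at least one serving, and adds "Safety outcomes will be evaluated on the ITT population". PP is reserved for efficacy, so no PP safety analysis is planned.

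**SAP.** Section 6 defines two sets only. ITT "includes all subjects who were enrolled and serves as the primary analysis population", with no dosing condition. PP is a subset of ITT, with compliance-type exclusions such as "Use of prohibited drugs or any products thought to alter the primary outcome variable during the study". Section 8 then says "All analyses will be conducted for the ITT and PP populations". The safety outputs come under that section, in 8.2: AEs and SAEs are described, and "The proportion of subjects with at least 1 possibly, probably, or definitely related AE will be estimated along with the corresponding 95% CI". No population is named for them there. The section headed "11. Changes from protocol" reads N/A.

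**The concern.** The two documents use one label, ITT, for two different sets. A programmer working from the SAP would divide by all enrolled subjects, while someone reading the report against the protocol would assume the denominator is participants who took the product.

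Two things follow. The main related-AE proportion can be diluted by people who never drank the product and so could not have a product-emergent event. A second proportion, on PP, also appears, although the protocol does not plan it. PP membership can depend on the AE itself: an event treated with an antidiarrheal, laxative or antibiotic (prohibited under protocol 8.3) can remove that participant from PP. With N/A in SAP 11, nothing tells the reader that the set has changed.

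**Working it through.** The plan gives no AE rate, run-in dropout rate or PP exclusion rate, so there is no stated figure to reproduce. The check compares the text first and then uses assumed counts for scale.

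**1. Can the two sets differ?** Yes.
- Eligible participants are enrolled at Visit 1, Day 0, and then start the run-in (protocol 7.2).
- The first serving is taken in clinic at Visit 2, Day 14 (protocol 7.2 and 11.2).
- Early terminations are not replaced (protocol 12.2, SAP 7).

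A person who leaves during run-in is therefore in the SAP's ITT set and not in the protocol's safety set.

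**2. Can such a person contribute an event?** No. Protocol 13.3 restricts reporting to product-emergent AEs after consumption, so this person enters the denominator only.

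**3. Size of the dilution.** Let x be participants with a related AE and d the run-in dropouts among 25 enrolled.
- SAP ITT proportion: x/25.
- Dosed-set proportion: x/(25 − d).
- Ratio of the two: (25 − d)/25, so the relative dilution is d/25 whatever x is.

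With x = 3 assumed, the SAP proportion is 3/25 = 12.0% (exact Clopper-Pearson 95% CI 2.5 to 31.2). Against it:

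| d | Dosed-set proportion | Exact 95% CI (%) | Gap (points) | Relative dilution d/25 |
|---|---|---|---|---|
| 0 | 3/25 = 12.0% | 2.5 to 31.2 | 0 | 0% |
| 1 | 3/24 = 12.5% | 2.7 to 32.4 | 0.5 | 4% |
| 2 | 3/23 = 13.0% | 2.8 to 33.6 | 1.0 | 8% |
| 3 | 3/22 = 13.6% | 2.9 to 34.9 | 1.6 | 12% |

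Sensitivity to x, for d = 1, 2 and 3:
- x = 1: gaps of 0.2, 0.3 and 0.5 points (1/24, 1/23 and 1/22, each less 1/25).
- x = 6: gaps of 1.0, 2.1 and 3.3 points (6/24, 6/23 and 6/22, each less 6/25).
- x = 0: both proportions are 0%, but the exact upper limit is 13.7% on 25 against 15.4% on 22.

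**4. The PP rate.** Its direction depends on who is excluded. Take 23 dosed participants and 3 cases, all assumed.
- If exclusions are unrelated to AEs, the expected PP rate equals the dosed rate, 3/23 = 13.0%.
- With 3 excluded at random, the hypergeometric chance that two or more of the 3 cases are lost is 0.0339 + 0.0006 = 0.03.
- With 8 excluded at random, that chance is 0.237 + 0.032 = 0.27, leaving 1/15 = 6.7% or 0/15 = 0%.
- If AEs or their treatment cause exclusions, the rate is pulled down.

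The documents do not say which of these applies.

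**The case against.** The strongest reply is that the section 8 sentence was written with the LcS outcomes in mind. It follows general statements on descriptive statistics and significance tests, and 8.2 limits the AE description to product-emergent events, which already implies dosing. That may be what was intended, but the SAP does not say it. Limiting which events count fixes the numerator and leaves the denominator at all enrolled. Protocol 2.2 also describes ITT in general terms without a dosing condition, but the Synopsis and 12.3 both give the operational definition, and both require a serving.

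The reply on consequence largely stands. Every dosed participant is inside the SAP's ITT set, so no dosed participant's AE is lost from that output. The sets are identical if nobody leaves in run-in. With 3 cases, the largest gap shown is 1.6 points, inside an interval about 29 points wide (2.5 to 31.2). Safety has no decision rule.

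Three stronger readings are tempting, and the documents do not support them:
- *A low PP rate would show that AEs caused the exclusions.* The PP criteria are broad and open-ended, and random exclusion alone can produce a low rate if enough people are excluded, as step 4 shows.
- *Vital signs have no safety set either.* On the same literal reading, any vital-signs summary would fall on ITT and PP. SAP 8.1 lists vital signs under "Subject demographic and anthropometric measures of enrolled subjects will include" and 8.2 specifies no post-baseline summary. That is an omitted summary, which is a separate matter from a population mismatch.
- *The report will certainly carry these denominators.* That depends on the programmers following section 8 to the letter.

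**Conclusion.** The mismatch holds on the text and is minor. As written, the SAP places the AE and SAE description and the related-AE proportion on all enrolled and on PP. The protocol specifies participants with at least one serving, and SAP 11 does not disclose the difference.

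The ITT dilution is d/25 in relative terms. With the assumed 3 cases and 0 to 3 run-in dropouts, it is 12.0% against 12.0% to 13.6%, with no effect at d = 0. Over 1 to 6 cases and 1 to 3 dropouts, the gap is 0.2 to 3.3 points, and the tabulated intervals overlap almost entirely. These sizes rest on assumed counts; only N = 25 comes from the documents. The PP safety rate is an unplanned addition that can leave participants out because of an AE or its treatment, but neither its direction nor its size can be established.

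The case for acting is that the stated rule departs from the protocol without saying so and is cheap to correct. The documents do not show that the safety conclusions would be materially wrong.

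**What to change.** 1. Add to SAP 6: *Safety population: all enrolled subjects who consumed at least one serving of study product.*
2. Replace the population sentence in SAP 8 with: *Demographic summaries and efficacy analyses will be conducted for the ITT and PP populations; demographic summaries will also be given for the Safety population. Safety analyses (product-emergent AEs, SAEs, related-AE proportion with 95% CI) will be conducted on the Safety population only.* This keeps demographics on every analysis population, as protocol 12.3.1 asks.
3. In SAP 11, replace N/A with the actual changes. Listing the ITT definition alone would make the section look complete when it is not. The list should include:
   - ITT is redefined from at least one serving consumed (protocol 12.3) to all enrolled (SAP 6.1).
   - The primary efficacy population changes from PP (protocol 12.3) to ITT (SAP 6.1).
   - Non-detectable counts change from zero (protocol 12.3.2) to the limit of detection (SAP 8.2).
   - Safety stays on the protocol's dosed set, now named the Safety population.

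The cost is a few lines of text, a third set to program and one extra demographic column, which duplicates ITT if nobody leaves in run-in. No new data, visits or staff are needed. The PP safety table, which the protocol did not plan, is lost.

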8.1. Demographic and anthropometric measures

Subject demographic and anthropometric measures of enrolled subjects will include:

- Collected at screening visit 1
 - o Age (years)
 - o Sex (Male, Female)

- o Ethnicity (Hispanic/Latino, Not Hispanic/Latino)
- Race (White, Black/African American, Asian, Native Hawaiian/Other Pacific Islander, American Indian/Alaskan Native, Other). Note "more than one race" will be used if more than one race is selected
- o Weight (kg)
- o Height (cm)
- \circ BMI (kg/m²)
- o Heart rate (bpm)
- Systolic blood pressure (mmHg)
- Diastolic blood pressure (mmHg)

8.2. Outcome analyses

For samples where LcS is not detected, counts will be set to the limit of detection to allow for statistical analysis¹. Descriptive plots will be provided for the distribution of LcS at each time point (i.e. boxplots) as well as line graphs for each subject. LcS number over time will be analyzed with a repeated measures model with an unstructured covariance structure where the LcS number at each time point will be included in the response vector. The model derived absolute change in LcS from baseline (day 14) to each of days 21, day 28, and 42 will be estimated along with the corresponding 95% confidence interval. In the event model assumptions are violated (i.e. constant variance and/or normality of residuals), a log transformation followed by a rank transformation will be considered. Note, if a rank transformation is used, contrast statements will be used to test the change from baseline but an estimate will not be calculated.

It is possible that the baseline LcS number for all subjects will be non-detectable which would likely result in the model assumption failure. If there are no detectable LcS levels at baseline and the repeated measure model assumptions are violated after exploring possible data transformations, then a model will be fit that only considers the post-consumption time points where the subject is on active product (day 21 and day 28). The estimated mean and 95% CI at day 21 and day 28 would then reflect an estimated increase from baseline. The proportion of subjects that return to baseline (day 14) by day 42 will be estimated along with a 95% CI. Additionally, in the subset of subjects that have elevated LcS while on study product measured at day 21 or day 28, as compared to baseline (day 14), the proportion of subjects that return to baseline by day 42 will be estimated along with a 95% CI.

Product emergent-AEs and SAE will be described. The proportion of subjects with at least 1 possibly, probably, or definitely related AE will be estimated along with the corresponding 95% CI.

9. Handling of missing data

For outcomes measured at multiple time points post baseline, statistical models that account for unbalanced data will be used. Specifically, missing data will be handled by maximum likelihood estimated of mixed models which assumes data is missing at random.

10. Deviations from statistical plan and other issues

During the analysis and reporting process, any deviations from the statistical analysis designed for this protocol will be described and justified.

11. Changes from protocol

N/A

12. References

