2.1 Abbreviations

AE adverse event

ANOVA analysis of variance BMI body mass index

C Celsius

CFR Code of Federal Regulations

CFU colony forming unit

d day(s)

DDC direct data capture
DNA deoxyribonucleic acid
eCRF electronic case report file
FDA Food and Drug Administration

g gram(s)

GCP Good Clinical Practice

GI gastrointestinal

GRAS generally recognized as safe

h hour(s)

HIPAA Health Insurance Portability and Accountability Act

ICH International Conference on Harmonization

IRB Institutional Review Board

ITT intent-to-treat kg kilogram

LeS Lacticaseibacillus paracasei strain Shirota

LOD limit of detection

mg milligram mL milliliter

mm Hg millimeter mercury

mo month(s)

NSAID non-steroidal anti-inflammatory drugs

OTC over the counter

oz ounce

PCR polymerase chain reaction

PP per protocol RNA ribonucleic acid

SAE Serious Adverse Event SD standard deviation

SEM standard error to the mean SMP specimen management plan SOP Standard Operating Procedures

wk week(s) y year(s)

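### The protocol synopsis, protocol 12.3.2 and SAP 8.2 disagree on the analysis scale and on non-detects while SAP 11 reports no change; SAP 8.2 starts on raw CFU/g and can end at ranks, with no estimate of the primary change

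*SAP*

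**What the plan says.** Three places describe the same analysis.

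- **Protocol synopsis (section 3), Statistical Analysis:** "The LcS number measured at each time point will be log-transformed and included in the response vector". Also "Non-detectable levels will be replaced by zero". The fallback is ranks.
- **Protocol 12.3.2:** "The LcS number measured at each time point will be included in the response vector", with no transformation at this step and the same zero coding. If assumptions fail, "a rank-based transformation or log transformation (if non-zero counts) will be considered". It promises: "The absolute change from baseline to each measured time point will be estimated along with the corresponding 95% confidence interval".
- **SAP 8.2:** untransformed counts in a repeated-measures model with unstructured covariance, non-detects set to the LOD, then "In the event model assumptions are violated (i.e. constant variance and/or normality of residuals), a log transformation followed by a rank transformation will be considered". If ranks are used, the change from baseline is tested by contrasts and no estimate is produced. A separate model of Days 21 and 28 only is available when no baseline is detectable and transformations have failed.

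Protocol 12.3 defers to the SAP: "Statistical analysis details for this study will be provided in a Statistical Analysis Plan". SAP 11 (Changes from protocol) is answered N/A. No LOD value appears in either document; the protocol has only the abbreviation entry "LOD limit of detection".

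**The concern.** There are two linked problems. First, the documents do not agree on scale or on the coding of non-detects, and the synopsis rule cannot be carried out as written for any non-detect. Non-detects are expected: SAP 8.2 itself allows that every baseline may be one. The SAP's move from zero to LOD departs from both protocol sections, and its raw starting scale departs from the synopsis, so N/A in SAP 11 is not correct.

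Second, the SAP chooses the scale after looking at residuals, gives no threshold for that decision, and starts from a scale that bacterial counts are unlikely to fit. The last step of the sequence gives up the quantity that the study exists to estimate. At stake are the size of the primary change, its 95% CI and its interpretation.

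**Working it through.** **Inputs from the documents.** N=25 (Protocol 12.2); primary endpoint is the Day 14 to Day 28 change in CFU/g (SAP 5.1); on-product level about 10^7 per gram in earlier studies (Protocol 4.4); two-sided 0.05 (SAP 8). N=25 has no stated effect size, SD or power, so there is no plan figure to reproduce.

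**Assumptions (not in the documents).** Day 28 log10 counts normal with mean 7 and SD 0.3 to 1.0; LOD 10^2 or 10^3; Shapiro-Wilk at 0.05 as the residual check; detectable baselines uniform on 3 to 5 log10.

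**Step 1: side by side.**

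| | Synopsis | Protocol 12.3.2 | SAP 8.2 |
|---|---|---|---|
| First scale | log | raw | raw |
| Non-detect | zero | zero | LOD |
| Fallback | rank | rank, or log if no zeros | log, then rank |

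**Step 2: coding.** On the raw scale, zero against 10^2 or 10^3 is trivial beside 10^7. On the log scale, log10(0) is undefined, while LOD coding gives a change of 7 − log10(LOD): 7 − 2 = 5.0, or 7 − 3 = 4.0. If all baselines are non-detectable, the estimate therefore moves one-for-one with log10 LOD.

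**Step 3: raw scale.** Simulated trials with all baselines at the LOD; t interval for the arithmetic mean change, whose true value is 10^7 × exp[(ln10 × SD)²/2] − LOD.

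| SD (log10) | Raw rejected | 95% CI coverage if raw is kept |
|---|---|---|
| 0.3 | 84% | 92% |
| 0.5 | 99% | 84% |
| 0.7 | 99.9% | 74% |
| 1.0 | 100% | 55% |

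**Step 4: is the rescue model open?** It needs all 25 baselines non-detectable. P(at least one detectable) = 1 − (1 − q)^25 = 22%, 40%, 72% for an assumed per-person chance q = 1%, 2%, 5%.

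**Step 5: does the log check fail?** This depends on the check, which the SAP does not define. With one detectable baseline among 24 constants:

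- Residuals standardised within visit: the odd value has a standardised residual of (n−1)/√n = 24/5 = 4.8, so rejection is about 100%.
- The paired Day 28 minus Day 14 log10 change: rejection is about 88%, 51% and 11% at SD 0.3, 0.5 and 1.0.

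With no detectable baseline, pooled residuals fail in 96% to 100% of trials. Standardising within visit and leaving out the constant baseline visit gives 4% to 11%.

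**Step 6: what remains if ranks are used?** The rank contrast test, per-visit descriptive statistics and plots, and two return-to-baseline proportions with CIs. None of these estimates the Day 14 to Day 28 change.

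**Step 7: the downside of fixing log10.** Suppose Day 28 samples are truly non-detectable at a rate of 2% or 5%, with LOD 10^2. The true mean change is 0.98 × 5 = 4.90 or 0.95 × 5 = 4.75. At SD 0.3 the log10 t interval covers it in about 78% and 73% of trials. Splitting by what is seen:

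- No Day 28 non-detect observed (probability 0.98^25 = 60%, 0.95^25 = 28%): coverage about 64% and 2%.
- At least one observed: above 99% in both cases.

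Across SD 0.3 to 1.0 the ranges are 2% to 92% and 98% to 99.9%.

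**The case against.** The strongest reply is that the SAP is operative by the protocol's own deferral, that ranks are only to be considered, and that a statistician would probably stop at the log model. The poor raw-scale coverage mostly belongs to a branch the plan would leave, because the check that reveals the problem also sends the analysis to log. All of that stands, and it limits the point. It does not make N/A in SAP 11 correct, supply an LOD, or guarantee an estimate. The undertaking in SAP 10 to explain later deviations does not cover a difference already present when the SAP was written.

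A reader might infer that one detectable baseline makes loss of the estimate near certain. The documents do not support that: no check is named, and the failure rate in step 5 runs from 11% to about 100% according to the check and the SD. The baseline detection rates are also assumed, and the protocol excludes fermented products during run-in.

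A reader might also infer that the rank route opens only when a baseline is detectable. It could be reached with all baselines non-detectable too, if the rank model were judged acceptable.

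Finally, a reader might think that a Hodges-Lehmann interval should take over whenever a Day 28 non-detect is seen. Step 7 shows the reverse: the log10 interval over-covers in those trials. Hodges-Lehmann also has a different target. At SD 0.3 with 5% non-detects its pseudo-median is 4.97, against a mean change of 4.75.

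**Conclusion.** The point holds and should be fixed. The conflict in scale and coding, the incorrect N/A, the missing LOD and the possible end without an estimate are all on the page and need no assumption. That raw CFU/g is a poor first scale rests on lognormal counts with SD 0.3 to 1.0, under which it would be rejected in 84% to 100% of trials. How likely the analysis is to finish at ranks cannot be stated from the documents; the supported wording is that it can. With an expected rise of several log10 units, the direction of effect is unlikely to change. What is exposed is the reported size of the primary change and its CI.

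**What to change.** 1. In the synopsis, protocol 12.3.2 and SAP 8.2, name log10 CFU/g, with non-detects set to a stated LOD, as the primary scale, with no switch after a residual check.
2. Always report the Day 14 to Day 28 log10 change and its 95% CI from the repeated-measures model already planned, fitted by maximum likelihood as in SAP 9.
3. If all baselines are non-detectable, use the Day 21/28 model on log10 count minus log10 LOD, and state the dependence on the LOD shown in step 2.
4. Make any rank analysis a pre-specified sensitivity analysis alongside the log10 estimate, never in place of it. If Hodges-Lehmann with a 95% CI is used, say that it estimates the pseudo-median of the log10 change. Do not give it precedence when a Day 28 non-detect is observed.
5. State the limitation: with a low true rate of Day 28 non-detects, the log10 interval can under-cover the mean overall, and this comes from trials in which none happens to be observed.
6. Enter the LOD coding and the scale change in SAP 11.

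The cost is wording in four places, one value from the laboratory and, if Hodges-Lehmann is added, minor programming. No new data are needed, and the raw mean can stay as a descriptive statistic. The statistical price is the limitation in item 5.
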